[37] Use of any opiate analgesic at average daily doses >30 mg/day of morphine or its equivalent or use of variable doses of any opiate analgesic within 6 weeks prior to baseline randomization. Exception for patients with pain that may interfere with undergoing an MRI: patient may receive premedication of ≤30 mg of morphine or equivalent, on the day of the MRI, for significant pain as judged by the investigator.

[38] Had a live vaccination within 12 weeks prior to baseline randomization, or intend to have a live vaccination during the course of the study, or within 12 weeks of completing treatment in this study, or have participated in a vaccine clinical study within 12 weeks prior to baseline randomization. Investigators are to review the vaccination status of their patients and follow the local guidelines for adult vaccination with nonlive vaccines intended to prevent infectious disease prior to therapy.

**Note:** Killed/inactive or subunit vaccines are expected to be safe; however, their efficacy with concomitant ixekizumab treatment is unknown.

[39] Had a vaccination with Bacillus Calmette-Guérin (BCG) within 12 months prior to baseline randomization, or intend to have this vaccination with BCG during the course of the study, or within 12 months of completing treatment in this study.

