### 5.3. Screen Failures

Individuals who do not meet the criteria for participation in this study (screen failure) may be rescreened in the following circumstances: patients who test positive for latent TB at screening may be rescreened following appropriate treatment as described in Section 8.4.6; patients who do not qualify at screening under Exclusion Criteria [14], [25], [40], or [54], may be rescreened one time,  $\geq 4$  weeks after documented resolution of symptoms or from time of blood donation.

Screening MRIs must be performed  $\leq 30$  days prior to baseline randomization (Visit 2). After consultation with Lilly medical, patients may be rescreened if screening MRI(s) of the spine and/or SIJ were performed  $> 30$  days prior to baseline randomization.

If a patient is unable to complete all screening procedures within the screening period, the patient may be rescreened after consultation with Lilly medical.

When rescreening is performed, the individual must sign a new informed consent form (ICF) and will be assigned a new identification number. To ensure all eligibility criteria are met, all screening procedures must be repeated unless previously conducted within timeframes specified in the Schedule of Activities ([Appendix 2](#)).

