#### **NSAIDs and Analgesics:**

##### Blinded Treatment Dosing Period (Period 2):

NSAIDs, including COX-2 inhibitors, will be allowed up to the maximum recommended doses for pain. Patients must be on a stable dose of NSAIDs/COX-2 inhibitors for at least 2 weeks prior to baseline randomization. Introduction of a new NSAID or dose adjustment to an existing NSAID is not permitted, unless required for safety reasons.

Short-acting analgesics with no anti-inflammatory action (such as paracetamol) are permitted and may be administered ad hoc as needed and are to be withheld within the 24-hour period prior to any assessment. Aspirin (dose not exceeding 350 mg/day) may be taken to manage cardiovascular risk.

Opiate analgesic use is allowed but not to exceed >30 mg/day of morphine or its equivalent. Patients are to be on stable dose during Period 2. Introduction of a new opiate analgesic or dose adjustment to an existing opiate analgesic is not permitted, unless required for safety reasons or as premedication for MRIs.

Extended Treatment and Post-Treatment Follow-Up Periods (Periods 3 and 4):

After completion of the Week 16 assessments, alterations of NSAIDs, including COX-2 inhibitors (dose change, introduction, or withdrawal) are allowed. Doses are recommended to be stable in the 2 weeks prior to an arthritis assessment.

Short-acting analgesics with no anti-inflammatory action (such as paracetamol) are permitted and may be administered ad hoc as needed but are to be withheld within the 24-hour period prior to any assessment. Aspirin (dose not exceeding 350 mg/day) may be taken to manage cardiovascular risk.

Use of variable doses of opiate analgesics is allowed, but not to exceed an average daily dose of 30 mg morphine or its equivalent.

**Conventional DMARDs:**Blinded Treatment Dosing Period (Period 2):

Discontinuation of excluded oral or injectable cDMARDs before study enrollment must occur at least 4 weeks prior to baseline. Methotrexate (oral or parenteral up to 25 mg/week), sulfasalazine (up to 3 g/day), or hydroxychloroquine (up to 400 mg/day) may be allowed IF at stable dose for at least 4 weeks prior to baseline randomization.

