- dd If MRI is conducted on the same day as study visit, ensure that any scales/questionnaires are completed prior to administering any premedication to facilitate patient undergoing an MRI (for example, morphine or equivalent for significant pain as judged by the investigator or a benzodiazepine for claustrophobia).
- ee For all patients, screening MRIs of the spine and SIJ must be completed  $\leq 30$  days prior to randomization (refer to Sections [5.3](#) and [5.4](#)).

---

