[31] Current use of oral corticosteroids > 10 mg/day prednisone or its equivalent	Exclude from PPS if 1. dose > 10 mg/day any time within 4 weeks; or 2. Stopped or decreased dose for a current med < 10 days before randomization; or 3. Increased dose for current one or started a new one < 4 wks before randomization;	Monitor and Stats
[32] Have received any prior, or are currently receiving, treatment with biologic or other immunomodulatory agents, including investigational therapies (such as but not limited to Janus kinase (JAK) inhibitors, TNF inhibitors, IL-1, IL-6, IL-23, IL-17 (including ixekizumab), IL-17R, T cell, or B cell targeted therapies).	Exclude from PPS	Monitor and Stats
[33] Are currently enrolled in, have participated, or discontinued from a clinical trial involving an investigational product or nonapproved use of a drug or device within the last 30 days prior to screening or a period of at least 5 half-lives of the last administration of the drug, whichever is longer	Exclude from PPS	Monitor

Important Protocol Deviation Category/Subcategory/Study Specific	Action for PPS Analysis	Source to Identify Protocol Deviation^a
[34] Are currently enrolled in any other clinical trial involving an investigational product or any other type of medical research judged not to be scientifically or medically compatible with this study	Exclude from PPS	Monitor
[35] Are currently receiving or have received treatment with denosumab within 6 months prior to baseline randomization.	Do not exclude from PPS	Monitor and Stats
[36] Have received any parenteral glucocorticoid administered by intra-articular, intramuscular, or IV injection within 6 weeks prior to baseline randomization, or a parenteral injection of glucocorticosteroids is anticipated during the Period 2.	Exclude from PPS	Monitor and Stats
[37] Use of any opiate analgesic at average daily doses >30 mg/day of morphine or its equivalent or use of variable doses of any opiate analgesic within 6 weeks prior to baseline randomization. For Japan patients, Use of pregabalin >300 mg/day or use of variable doses of pregabalin within 2 weeks prior to baseline randomization.	Exclude from PPS If 1. doses >30 mg/day any time within 6 weeks before randomization; or 2. Stopped or decreased dose for a current one <7 days before randomization; or 3. Increased dose for current one or started a new one <6 wks before randomization	Monitor and Stats

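### The per-protocol rule for opiates (SAP Table RHBV.6.12, row [37]) omits the protocol's MRI-day premedication exception, so as written it excludes patients who followed the protocol

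*SAP*

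**What the plan says.** Protocol Section 5.2, exclusion [37], bars average opiate use above 30 mg/day of morphine or equivalent, and variable opiate dosing, in the 6 weeks before randomization. It then gives an "Exception for patients with pain that may interfere with undergoing an MRI", under which the "patient may receive premedication of ≤30 mg of morphine or equivalent, on the day of the MRI". Section 6.8 makes the same allowance during Period 2, where a new opiate or a dose change is not permitted "unless required for safety reasons or as premedication for MRIs".

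On timing, Appendix 2 footnote ee says that "screening MRIs of the spine and SIJ must be completed" no more than 30 days before randomization. Protocol Section 5.3 says the same.

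SAP Section 6.15, Table RHBV.6.12, row [37], restates the criterion without the MRI exception. It excludes a patient from the PPS if any one of three conditions is met:

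1. "doses >30 mg/day any time within 6 weeks before randomization"
2. "Stopped or decreased dose for a current one <7 days before randomization"
3. "Increased dose for current one or started a new one <6 wks before randomization"

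The row's source is Monitor and Stats. The table footnote explains that a deviation is shown when either the monitors' list or the database program finds it.

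**The concern.** The PPS is meant to remove patients whose departures from the protocol could affect the primary endpoint. SAP Section 6.15 treats important deviations as violations of the protocol, and Section 6.1.5 builds the PPS by removing a subset of them. A dose that the protocol permits is not a violation, yet condition 3 of row [37] has no wording that spares it.

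Two outputs are exposed: the PPS analyses of ASAS40 and ASAS20, and the table and listing of important deviations. The patients concerned are those whose pain might interfere with an MRI. That trait is plausibly related to an endpoint built on patient-reported spinal pain, function and stiffness, so they are not an arbitrary subset.

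**Working it through.** **Inputs**

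- Permitted screening-MRI days: 0 to 30 days before randomization, which is 31 possible days (Protocol Section 5.3; Appendix 2 footnote ee).
- Look-back for conditions 1 and 3: 6 weeks = 6 × 7 = 42 days (SAP row [37]).
- Look-back for condition 2: less than 7 days (SAP row [37]).
- Permitted premedication: at most 30 mg morphine or equivalent, on the MRI day (Protocol exclusion [37]).
- Design: 80 per arm, ASAS40 44% against 16%, two-sided Fisher's exact test at 0.05, stated power about 96% (SAP Section 5.3).

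**Which conditions a permitted dose meets**

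| Condition | Test | Result |
|---|---|---|
| 3 (newly started) | MRI day < 42 | Met on 31 of 31 permitted days for a patient not already on an opiate |
| 2 (stopped) | MRI day < 7 | Could be met on days 0 to 6, but only if a single dose counts as a current medication that was then stopped |
| 1 (>30 mg/day) | Daily total > 30 mg | Not met by the premedication alone; possible if it is added to a standing opiate |

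To illustrate condition 1, a standing 20 mg plus 30 mg gives 50 mg on the MRI day. That patient would also have an increased dose under condition 3. The documents do not say whether the 30 mg limit on premedication is in addition to a standing dose. Condition 3 therefore carries the point by itself.

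**Can a program detect the dose?** Protocol Section 6.8 requires all concomitant medication to be entered in the eCRF, so the premedication should be in the database. Because either source is enough, a monitor's judgement that the dose was permitted would not remove a programmed flag.

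**Size**

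First, the plan's own figure. Power is the sum over all i, j of Bin(i; 80, 0.44) × Bin(j; 80, 0.16), counting only the tables with Fisher p ≤ 0.05. The result is 96.7%, which reproduces the stated 96% or so.

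The documents give no premedication rate. The range below is an assumption. It spreads the losses evenly over the arms, keeps the response rates unchanged and ignores all other PPS exclusions.

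| Assumed share | Of 320 | n per arm | Power |
|---|---|---|---|
| 0% | 0 | 80 | 96.7% |
| 1% | 3.2 | 79 | 96.5% |
| 2% | 6.4 | 78 | 96.4% |
| 5% | 16 | 76 | 95.9% |
| 10% | 32 | 72 | 94.9% |

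With the exception carried into row [37], no patient would leave the PPS for permitted premedication alone.

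**The case against.** The strongest answer is that the table is shorthand, read in order: the first column names a deviation and the second says what to do about it. The bracketed number points to protocol criterion [37], exception included. Since an important deviation must be a violation, permitted premedication never reaches the three conditions. Row [30] also omits a protocol allowance, the one for stable methotrexate, sulfasalazine or hydroxychloroquine, and nobody would call all those patients deviators.

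Part of this stands. A reader who applies the definition in Section 6.15 first would keep the patient. But row [30] differs where it matters. Its exclusion conditions test for recent dose changes and for combination use, so a patient on a stable single agent passes and the allowance survives. In row [37] it is the exclusion condition itself that contradicts the exception. The SAP revision history also shows that the PPS conditions for [37] were revised after Version 1, and the exception is still absent.

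Four further points stand:

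- The revision history says the programming guidance was moved to an external document, which may already filter MRI-day doses.
- The premedication rate is not in the documents.
- The use precedes randomization, so exclusion for it cannot depend on the assigned arm and gives no direct reason for bias in the ixekizumab–placebo contrast.
- The PPS analyses are supportive and outside the multiplicity procedure.

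A reader might infer that all three conditions exclude every premedicated patient. The text does not support that: the permitted dose cannot meet condition 1 alone, and condition 2 concerns an opiate already in current use. A reader might also extend the point to premedication for the Week 16 MRI. That falls under the excluded con-meds row and Appendix 13, which is not readable in the public SAP, so nothing can be concluded about it.

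**Conclusion.** The point holds as an inconsistency in the text. Condition 3 of row [37], as written, conflicts with protocol exclusion [37] and with the SAP's own account of what a deviation is. It covers every permitted screening-MRI day for a patient not already on an opiate.

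The documents do not show that compliant patients were actually removed, how many there might be, or that the PPS estimate moved in any direction. It is tempting to say that the PPS is shifted toward less painful disease; that is a plausible direction without a figure behind it. The loss of precision is minor: across the assumed 1% to 10% range, power falls by 0.2 to 1.8 percentage points. The reason to act is that the PPS should mean what the SAP says it means and that permitted use should not be counted as an important deviation. The ITT primary analysis and the confirmatory testing are untouched.

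**What to change.** Reconcile row [37] of Table RHBV.6.12, and the programming specification behind it, with the protocol. One sentence is enough: premedication that falls under the existing MRI-day exception of protocol criterion [37] is disregarded in conditions 1 to 3 and in the deviation count. This introduces no new clinical rule. If the external guidance already does this, say so in the SAP.

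The direct cost is that sentence and a filter matching opiate records to the MRI date. There is also a procedural cost. SAP Version 3 was approved after unblinding, so any change to PPS membership now is a post-unblinding change to an analysis set. Document it as alignment with the protocol and report, by arm, how many patients change PPS status. If none do, state that and the matter is closed.

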### 9.2.4. *Analysis Populations*

The following analysis populations will be used:

**Intent-to-Treat Population (ITT):** Unless otherwise specified, efficacy and health outcomes analyses for Period 2 will be conducted on the ITT population, defined as all randomized patients, even if the patient does not take the assigned treatment, does not receive the correct treatment, or otherwise does not follow the protocol. Patients will be analyzed according to the treatment to which they were assigned.

**Per-Protocol Set (PPS):** In addition, the primary efficacy analysis will be repeated using the PPS, which is defined as all randomized patients who are compliant with therapy, who do not have significant protocol deviations, and whose investigator site does not have significant GCP issues that require a report to the regulatory agencies prior to Week 16 (Visit 8). Compliance with therapy is defined to be missing no more than 20% of expected doses, not missing 2 consecutive doses (all injections at a visit are counted as 1 dose) and not have any occurrence of double-dosing (that is, took more injections at the same time point than specified in the protocol) during Period 2.

Significant protocol deviations will be described in the SAP. Patients will be analyzed according to the treatment to which they were assigned.

**Safety Population:** Safety analyses for Period 2 will be conducted on the Safety Population, defined as all randomized patients who received at least 1 dose of study treatment. Patients will be analyzed according to the treatment to which they were assigned in that period.

**Extended Treatment Period Population:** Efficacy, health outcomes, and safety analyses for Period 3 will be conducted on the Extended Treatment Period Population, defined as all patients who received at least 1 dose of ixekizumab treatment during Period 3.

**Follow-Up Population:** Safety analyses for Period 4 will be conducted on the Follow-Up Population, defined as all randomized patients who received at least 1 dose of study treatment and have entered the Period 4. Patients will be analyzed according to the treatment they received before entering the Period 4.

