NRS	numeric rating scale
NSAID	nonsteroidal anti-inflammatory drug
PK/PD	pharmacokinetics/pharmacodynamics
PPS	per-protocol set: The set of data generated by the subset of patients who sufficiently complied with the protocol to ensure that these data would be likely to exhibit the effects of treatment, according to the underlying scientific model.
Q2W	every 2 weeks
Q4W	every 4 weeks
rad-axSpA	radiographic axial spondyloarthritis: a subset of axSpA in which there is evidence of disease features on radiographic imaging
SAE	serious adverse event
SAP	statistical analysis plan
screen	The act of determining if an individual meets minimum requirements to become part of a pool of potential candidates for participation in a clinical study.
SF-36 MCS	Short Form 36 mental component score
SF-36 PCS	Short Form 36 physical component score
SIJ	sacroiliac joints
SpA	spondyloarthritis
SPARCC	Spondyloarthritis Research Consortium of Canada
SPARCC SSS	Spondyloarthritis Research Consortium of Canada–SIJ Structural Score
TEAE	treatment-emergent adverse event: Any untoward medical occurrence that either occurs or worsens at any time after treatment baseline and that does not necessarily have to have a causal relationship with this treatment.

---

Term	Definition
TNFi	tumor necrosis factor inhibitor
WPAI-SpA	Work Productivity Activity Impairment–Spondyloarthritis

---

---

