6.1.5. Analysis Populations

The following major analysis populations will be used (additional analysis populations for specific analysis will be defined in the corresponding analysis section):

Intent-to-Treat Population (ITT Population): Unless otherwise specified, efficacy and health outcomes analyses for Period 2 will be conducted on the ITT Population, defined as all randomized patients, even if the patient does not take the assigned treatment, does not receive the

correct treatment, or otherwise does not follow the protocol. Patients will be analyzed according to the treatment to which they were assigned.

Per-Protocol Set (PPS): In addition, the primary efficacy analysis will be repeated using the PPS, which is defined as all randomized patients who are compliant with therapy, who do not have a subset of important protocol deviations that impact the primary efficacy endpoint (Section 6.15), and whose investigator site does not have significant good clinical practice (GCP) issues that require a report to the regulatory agencies prior to Week 16 (Visit 8). Compliance with therapy is defined to be missing no more than 20% of expected doses, not missing 2 consecutive doses (all injections at an injection week are counted as 1 dose), and not have any occurrence of over-dosing (that is, took more injections at the same time point than specified in the protocol) during Period 2.

Patients will be analyzed according to the treatment to which they were assigned.

Safety Population: Safety analyses for Period 2 will be conducted on the Safety Population, defined as all randomized patients who received at least 1 dose of study treatment. Patients will be analyzed according to the treatment to which they were assigned in that period.

Extended Treatment Period Population: Efficacy, health outcomes, and safety analyses for Period 3 will be conducted on the Extended Treatment Period Population, defined as all patients who received at least 1 dose of ixekizumab treatment during Period 3.

Adalimumab Washout Population: Treatment-emergent adverse event analyses for Period 3 from Week 16 to Week 20 will be conducted on the Adalimumab Washout Population, defined as all patients who were randomized to adalimumab at Week 0 and took at least 1 placebo dose from Week 16 through Week 20.

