[D9] Patient develops any condition or contraindication as addressed in the local labeling for adalimumab	Exclude from PPS when occurred in Period 2	Monitor
[D12] Lilly stopped the patient participation	Do not exclude from PPS	Monitor
[D13] Patient became HBV DNA positive	Do not exclude from PPS	Monitor
[D14] Patient has a confirmed diagnosis of PCP during the study for patients from Japan sites	Do not exclude from PPS	Monitor
Category: Study Procedures		
Subcategory: Excluded Con-meds	Exclude from PPS (Excluded Con-meds refers to clinically meaningful change in con-meds (Appendix 13) occurred during Period 2 and prescribed for primary study condition] Excluded Con-meds in Period 3 refer to the lists in Appendix 13	Monitor and Stats
Subcategory: Lab/Imaging Criteria		

Important Protocol Deviation Category/Subcategory/Study Specific	Action for PPS Analysis	Source to Identify Protocol Deviation^a
Missing imaging as per protocol schedule of events	Do not exclude from PPS	Monitor
Missing lab chemistry and hematology: missing baseline or not having at least 1 postbaseline	Do not exclude from PPS	Stats
Subcategory: Other		
Missing QIDS total score: missing baseline or any scheduled visit prior to discontinuation visit	Do not exclude from PPS	Stats
Missing Columbia scale at any visit except Visit 1	Do not exclude from PPS	Monitor and Stats
Missing ASAS components for ASAS40 derivation: not having Week 16 measurement for patients who have completed Week 16	Do not exclude from PPS. Note: if missing ASAS components lead to missing ASAS40, such patient will be treated as nonresponder for the Week 16 ITT analyses	Stats
Had unqualified site personnel perform clinical safety and/or efficacy assessments	Do not exclude from PPS	Monitor
Category: Investigational Product		
Subcategory: Treatment Assignment/Randomization Error		
Took incorrect study medication	Do not exclude from PPS. Analyze 'As randomized' or 'As assigned'.	Stats and monitor
Subcategory: Compliance	Exclude from PPS when occurred during Period 2	Stats
Subcategory: Patient took medication not fit for use	Do not exclude from PPS	Monitor
Subcategory: Other		
Randomized but did not take any study medication	Exclude from PPS	Stats
Category: Safety		
Subcategory: SAEs	Do not exclude from PPS	Monitor
Category: Informed Consent		
Subcategory: Informed Consent not Obtained/Missing/Late	Exclude from PPS	Monitor and Stats
Subcategory: Improper Informed Consent	Do not exclude from PPS	Monitor

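### The per-protocol set keeps patients who took incorrect study medication, with no limit on extent, which does not fit the SAP's own exclusion criterion

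*SAP*

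**What the plan says.** In SAP Section 6.15, Table RHBV.6.12, under Investigational Product, the entry "Took incorrect study medication" carries the action "Do not exclude from PPS. Analyze 'As randomized' or 'As assigned". The row sets no number of wrong doses, no duration and no study period.

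SAP Section 6.1.5 builds the PPS from randomised patients who comply with therapy, who are free of a "subset of important protocol deviations that impact the primary efficacy endpoint", and whose site has no reportable GCP problem. It adds: "Patients will be analyzed according to the treatment to which they were assigned". Protocol Section 9.2.4 describes the set as "all randomized patients who are compliant with therapy, who do not have significant protocol deviations", and leaves the description of significant deviations to the SAP. Protocol Appendix 1 gives the purpose of the set: it is the "subset of patients who sufficiently complied with the protocol to ensure that these data would be likely to exhibit the effects of treatment".

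On use, SAP Section 6.1.5 states: "In addition, the primary efficacy analysis will be repeated using the PPS". Tables RHBV.6.1 and RHBV.6.5 extend the PPS to ASAS20. Protocol Section 9.4.1 makes the PPS analysis supportive of an ITT primary analysis.

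**The concern.** A per-protocol analysis is useful when it differs from ITT in the patients whose treatment departed from the plan. A patient who took another arm's product cannot show the effect of the assigned one, yet stays in the PPS under the assigned label. Lesser departures exclude: one over-dosing occurrence, or two consecutive missed doses, is enough. The ITT definition also keeps patients who received the wrong treatment, so on this deviation the two sets are identical and agreement between them carries no information.

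What is at stake is the sharpness of the supportive ASAS40 and ASAS20 analyses. The primary test is not affected.

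**Working it through.** **Step 1: does another rule remove these patients?**

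- SAP Section 6.1.5 defines compliance by three tests: the share of doses missed, consecutive missed doses, and over-dosing. None concerns which product was given.
- SAP Section 6.8 counts administered injections from the eCRF item on whether the dose was given. A Period 2 completer is due 3 + 2 × 7 = 17 injections. A patient who took all 17 from another arm's kits would score 100%.
- Other rows of Table RHBV.6.12 exclude non-compliance in Period 2 and patients never dosed. Neither covers a patient who was fully dosed with the wrong product.

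Nothing else in the plan removes such a patient.

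**Step 2: the plan's own figure.** Inputs from Protocol Section 9.1: 80 per arm, ASAS40 44% for ixekizumab Q2W and 16% for placebo, two-sided Fisher's exact test at 0.05, power about 96%. Full enumeration of the test gives 96.7%, so the stated figure is reproduced.

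**Step 3: dilution from retained patients.** The documents give no misdosing rate, so *k*, the number misdosed out of 80, is an assumption. The worst case is taken: each such patient received the opposite treatment throughout and responds at that arm's full rate.

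- One-way (*k* ixekizumab patients took placebo): difference = 28.0 − *k* × 28/80 = 28.0 − 0.35*k* points.
- Swap (*k* in each arm): difference = 28.0 − 0.70*k* points.

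Power repeats the Fisher enumeration with the affected arm as a sum of two binomials.

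| *k* of 80 | One-way difference | Power | Swap difference | Power |
|---|---|---|---|---|
| 0 | 28.0 | 96.7% | 28.0 | 96.7% |
| 1 | 27.65 | 96.4% | 27.3 | 95.9% |
| 2 | 27.3 | 96.0% | 26.6 | 94.9% |
| 4 | 26.6 | 95.2% | 25.2 | 92.4% |
| 8 | 25.2 | 93.1% | 22.4 | 84.7% |
| 16 | 22.4 | 87.0% | 16.8 | 58.2% |

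Up to 4 of 80 (5%), the shift is 1.4 points one-way or 2.8 points for a swap. It becomes material only at 10% to 20%.

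**Step 4: what exclusion costs.** Removing the misdosed patients returns the expected difference to 28.0 points. With 4 removed from the ixekizumab arm, power is 97.1%; with 4 removed from each arm it is 95.9%. (The first value exceeds 96.7% only because the exact test is discrete.)

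Two limits apply. The documents give no PPS size, so 80 is the randomised arm; in a smaller PPS the shift per patient is 28/*n*, slightly larger. Also, the PPS model is logistic regression, so the Fisher power figures only indicate scale.

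**The case against.** A reader might infer that this row contradicts the protocol's PPS definition, or that it defeats the purpose of the set. The documents do not support either reading.

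- The operative definition, Protocol Section 9.2.4, hands the list of significant deviations to the SAP, and Table RHBV.6.12 is that list. The same section prescribes as-assigned labelling for the PPS, so the label is not a SAP error. What remains is that the list should follow the SAP's own endpoint-impact criterion and the purpose stated in Appendix 1. Labelling says how members are analysed; it does not decide who belongs.
- The set still excludes non-compliance, patients never dosed, many eligibility failures, clinically meaningful changes in concomitant medication, missing consent and sites with GCP problems.
- The PPS is one of several supports. The SAP also plans Fisher's exact test, a categorical repeated-measures model, placebo multiple imputation, a tipping-point analysis and a summary that uses data after discontinuation. For mix-ups with placebo, retention pulls a superiority comparison towards no difference, so it cannot manufacture support.
- Sites confirm each package number in the IWRS (Protocol Section 6.2), which makes sustained misdosing less likely. The row could also cover a single wrong syringe, for which the worst case above is far too severe.

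These points limit the size of the issue. They do not explain why a patient wholly on another product meets the SAP criterion while one with two consecutive missed doses fails it, and the row gives no reason.

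**Conclusion.** The inconsistency is real and minor. Table RHBV.6.12 keeps patients who took incorrect medication in the PPS without limit on extent, against the criterion in SAP Section 6.1.5 and the purpose in Protocol Appendix 1, and the compliance rule does not close the gap.

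The bias is towards no difference and at most about 0.35 points per fully misdosed patient. That figure rests on 80 per arm, 44% versus 16% (stated for Q2W only), and complete exposure to the opposite treatment. A mix-up between the two ixekizumab regimens, or a few wrong doses, would probably matter less. The number of affected patients is unknown from the documents and likely to be small. The ITT primary conclusion does not depend on this row.

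**What to change.** Change the action for this row so that patients who received, in Period 2, a product other than the one assigned are excluded from the PPS. Several other rows already limit exclusion to Period 2. A wrong kit with the same content need not exclude. Keep as-assigned labelling for everyone who remains in the PPS and for ITT.

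Timing matters. SAP Section 3 records that Version 3 was approved after unblinding, and its list of changes since Version 2 does not mention Section 6.15, so the rule appears to predate unblinding. Redefining the set now would be a post hoc change. Report the narrower set as a labelled additional PPS sensitivity analysis beside the planned one, with the number of affected patients by arm.

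The cost is one further run of the PPS model and a slightly smaller set. The table already assigns identification of this deviation to both statistical programming and monitoring, so the main extra work is to check, for each case, whether the product differed.
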